7 INVESTIGATIONAL PRODUCT

7.1 Pembrolizumab (KEYTRUDA®)

Pembrolizumab is a humanized monoclonal antibody that blocks the interaction between PD-1 and its ligands, PD-L1 and PD-L2. Pembrolizumab is an IgG4 kappa immunoglobulin with an approximate molecular weight of 149 kDa.

7.1.1 Active Substance and Source

Product Name & Potency	Dosage Form
Pembrolizumab 50 mg	Lyophilized Powder for Injection
Pembrolizumab 100 mg/ 4mL	Solution for Injection

KEYTRUDA for injection is a sterile, preservative-free, white to off-white lyophilized powder in single-use vials. Each vial is reconstituted and diluted for intravenous infusion. Each 2 mL of reconstituted solution contains 50 mg of pembrolizumab and is formulated in L-histidine (3.1

mg), polysorbate 80 (0.4 mg), and sucrose (140 mg). May contain hydrochloric acid/sodium hydroxide-adjust pH to 5.5.

KEYTRUDA injection is a sterile, preservative-free, clear to slightly opalescent, colorless to slightly yellow solution that requires dilution for intravenous infusion. Each vial contains 100 mg of pembrolizumab in 4 mL of solution. Each 1 mL of solution contains 25 mg of pembrolizumab and is formulated in: L-histidine (1.55 mg), polysorbate 80 (0.2 mg), sucrose (70 mg), and Water for Injection, USP.

7.1.2 Drug Shipment

Pembrolizumab will be provided by Merck & Co., Inc. and shipped to the participating site. The investigational drug will be labeled in accordance with regulatory requirements (Drug identity, i.e., name, strength) is included in the label.

The date of receipt and the amount of drug received will be documented. Drug shipment records will be retained by the investigational pharmacist or designee.

7.2 Preparation

Refer to the package insert.

7.3 Storage and Stability

The Investigator or designate will be responsible for ensuring that the investigational product is securely maintained in a locked, limited-access facility, as specified by the Sponsor and in accordance with the applicable regulatory requirements.

Drug storage temperature will be maintained and recorded, as applicable.

KEYTRUDA for injection (lyophilized powder): Store vials under refrigeration at 2°C to 8°C (36°F to 46°F).

KEYTRUDA injection (solution): Store vials under refrigeration at 2°C to 8°C (36°F to 46°F) in original carton to protect from light. Do not freeze. Do not shake.

Refer to Investigator's Brochure/ package insert for storage and stability requirements.

7.3.1 Handling and Disposal

The Investigator or designee will be responsible for dispensing and accounting for all investigational drug provided by Merck & Co., Inc., exercising accepted medical and pharmaceutical practices. Study drugs must be handled as cytotoxic agents and appropriate precautions taken per the institution's environmentally safe handling procedures. All investigational drugs will be dispensed in accordance with the Investigator's prescription or written order.

All products dispensed will be recorded on a product accountability record. Records of product lot numbers and dates received will be entered on a product accountability form. This record will be reviewed by the Sponsor's staff or representative during periodic monitoring visits. It is the

Investigator's responsibility to ensure that an accurate record of investigational drug issued and returned is maintained.

All unused and/or partially used investigational drug will be destroyed according to standard practices after properly accounting for the dispensing. Partially used vials of study drug will not be re-used for other participants.

Under no circumstances will the Investigator supply investigational drug to a third party or allow the investigational drug to be used in a manner other than as directed by this protocol.

7.3.2 Overdose

For purposes of this trial, an overdose of pembrolizumab will be defined as any dose of 1,000 mg or greater (≥ 5 times the indicated dose). No specific information is available on the treatment of overdose of pembrolizumab.

In the event of overdose, the participant should be observed closely for signs of toxicity. Appropriate supportive treatment should be provided if clinically indicated.

7.4 Cetuximab

Please refer to package insert. This will be commercially supplied. As per the package insert, an intravenous anti-histamine (H_1 antagonist), namely Benadryl 50 mg intravenously, will be administered unless otherwise specified.

8 STUDY PROCEDURES

The study-specific assessments are detailed in this section and outlined in **Table 4** (Schedule of Procedures and Observations). Baseline and/or Screening assessments must be performed within **14** days prior to the first dose of investigational product. Any results falling outside of the reference ranges may be repeated at the discretion of the investigator. All on-study visit procedures are allowed a **window of ± 3 days** unless otherwise noted.

Informed consent **MUST** be completed prior to receiving any study related procedures.

8.1 Participant Registration

8.2 Baseline Evaluations

The following will be performed within 2 weeks prior to first dose of study drug:

- Medical history (including all prior anti-tumoral therapy related to cancer)
- Physical examination (standard of care)
- Vital signs (i.e., temperature, heart rate, respiratory rate, blood pressure, body weight, and height)
- ECOG Performance Status (**Appendix B**)
- Urinalysis

- Hematology (complete blood count (CBC) with automated differentials)
- CMP (complete metabolic panel) + Mg: chloride, CO₂, potassium, sodium, BUN, glucose, calcium, creatinine, total protein, albumin, total bilirubin, alkaline phosphatase, AST, ALT, A/G ratio, BUN/creatinine ratio, osmol (Calc), anion gap), magnesium.
- Thyroid function tests: TSH, Total T3, Free T4
- Baseline imaging with 30 days of the first dose of study drug: Preferred CT imaging (chest/abdomen/pelvis with contrast). A non-contrast CT chest and MRI abd/pelvis is an acceptable alternative if a contrast enhanced CT cannot be performed.
- Pregnancy test (serum) in females of childbearing potential (at baseline and then every 6 months, see Tables 4 and 5)
- Concomitant Medications: List any medications that are ongoing, or that will be discontinued, within 1 week prior to first dose of study drug.
- Adverse Events
- Tumor biopsy (within 30 days of Cycle 1 day 1)
- Tumor molecular status: Document prior tumor mismatch repair (MMR) testing and/or microsatellite instability (MSI) testing. Either test is acceptable. If neither has been performed, these should be performed, per local protocol.

8.3 Evaluations Performed on Treatment, Every Cycle, Day 1 (± “3” days)

- Physical examination (standard of care)
- Vital signs (i.e., temperature, heart rate, respiratory rate, blood pressure, body weight)
- Hematology (complete blood count (CBC) with automated differentials)
- CMP (complete metabolic panel) + Mg: chloride, CO₂, potassium, sodium, BUN, glucose, calcium, creatinine, total protein, albumin, total bilirubin, alkaline phosphatase, AST, ALT, A/G ratio, BUN/creatinine ratio, osmol (Calc), anion gap), magnesium.
- Thyroid function tests: TSH, Total T3, Free T4 (beginning with Cycle 2, every other cycle, i.e. cycles 2, 4, 6, 8, etc...)
- CEA
- Restaging imaging, to occur every 9 weeks from cycle 1, day 1 (+/- 7 days): Preferred CT imaging (chest/abdomen/pelvis with contrast). A non-contrast CT chest and MRI abd/pelvis is an acceptable alternative if a contrast enhanced CT cannot be performed.
- Blood biomarker (Cycle 1 day 1, Cycle 2 day 1, and Cycle 4 day 1 only)
- Concomitant Medications: List any medications that are ongoing, or that will be discontinued, within 1 week prior to first dose of study drug.
- Adverse events

- Tumor biopsy (Cycle 4 day 1, \pm 7" days)

8.4 Evaluations Performed on Treatment Day 15, cycle 1 only.

- Vital signs (i.e., temperature, heart rate, respiratory rate, blood pressure, body weight)
- BMP (basic metabolic panel) + Mg: chloride, CO₂, potassium, sodium, BUN, glucose, calcium, creatinine, A/G ratio, BUN/creatinine ratio, osmol (Calc), anion gap, magnesium.
- Directed physical exam
- Concomitant Medications
- Adverse Events

8.5 Evaluations Performed on Treatment, Every Cycle, Days 8, 15 (\pm "3" days)

- Vital signs (i.e., temperature, heart rate, respiratory rate, blood pressure, body weight)
- BMP (basic metabolic panel) + Mg: chloride, CO₂, potassium, sodium, BUN, glucose, calcium, creatinine, A/G ratio, BUN/creatinine ratio, osmol (Calc), anion gap, magnesium.

8.6 Evaluations Performed at End of Treatment (Off Treatment Visit)

The following evaluations will be performed at the end of treatment or at time of treatment discontinuation:

- Physical examination, including vital signs (i.e., temperature, heart rate, respiratory rate, blood pressure, body weight)
- Hematology [(i.e., complete blood count (CBC) with automated differentials)]: WBC, RBC, HGB, HCT, platelet, MCV, MCH, MCHC, % neutrophils, absolute neutrophils, , % monocytes, absolute monocytes, % eosinophils, absolute eosinophils, % basophils, absolute basophils, % lymphocyte, absolute lymphocyte, platelet confirmation (as clinically indicated), and differential confirmation (as clinically indicated).
- CMP +Mg (i.e., complete metabolic panel: chloride, CO₂, potassium, sodium, BUN, glucose, calcium, creatinine, total protein, albumin, total bilirubin, alkaline phosphatase, AST, ALT, A/G ratio, BUN/creatinine ratio, osmol (Calc), anion gap), Magnesium
- Thyroid function tests: TSH, Total T3, Free T4
- ECOG Performance Status (**Appendix B**)
- Concomitant medication: List any ongoing medications with dose changes, as applicable.
- Adverse events

8.7 Safety Follow-Up Evaluations

Follow-up safety evaluations will occur 30 days (\pm 7 days) after last dose of study drug or until resolution of any drug-related toxicity.

- Physical examination, including vital signs (i.e., temperature, heart rate, respiratory rate, blood pressure, body weight)
- Hematology [(i.e., complete blood count (CBC) with automated differentials)]: WBC, RBC, HGB, HCT, platelet, MCV, MCH, MCHC, % neutrophils, absolute neutrophils, , % monocytes, absolute monocytes, % eosinophils, absolute eosinophils, % basophils, absolute basophils, % lymphocyte, absolute lymphocyte, platelet confirmation (as clinically indicated), and differential confirmation (as clinically indicated).
- CMP (i.e., complete metabolic panel: chloride, CO₂, potassium, sodium, BUN, glucose, calcium, creatinine, total protein, albumin, total bilirubin, alkaline phosphatase, AST, ALT, A/G ratio, BUN/creatinine ratio, osmol (Calc), anion gap) + Magnesium
- Thyroid function tests: TSH, Total T3, Free T4
- Concomitant medications: List any ongoing medications with dose changes, as applicable.

8.8 Adverse events Safety Follow-up #2

A second follow-up safety evaluation will occur 60 days (\pm 7 days) after last dose of study drug, with blood work only being required (to follow-up on electrolytes).

- CMP (i.e., complete metabolic panel: chloride, CO₂, potassium, sodium, BUN, glucose, calcium, creatinine, total protein, albumin, total bilirubin, alkaline phosphatase, AST, ALT, A/G ratio, BUN/creatinine ratio, osmol (Calc), anion gap) + Magnesium

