6.1.1 Pembrolizumab

Dose Selection

Pembrolizumab 200 mg will be administered as a 30 minute IV infusion every 3 weeks. Sites should make every effort to target infusion timing to be as close to 30 minutes as possible. However, given the variability of infusion pumps from site to site, a window of 5 minutes and +10 minutes is permitted (i.e., infusion time is 30 minutes: -5 min/+10 min).

The package insert contains specific instructions for the preparation of the pembrolizumab infusion fluid and administration of infusion solution.

Timing of Dose Administration

Trial treatment will be administered on Day 1 of each cycle after all procedures/assessments have been completed (as detailed in **Table 4** Schedule of Procedures and Observations). Of note, the results of laboratory tests which are send-out tests (including TFTs) are not necessary prior to treatment. Pembrolizumab is to be administered after cetuximab infusion is complete. Trial treatment may be administered up to 3 days before or after the scheduled Day 1 of each cycle due to administrative reasons.

All trial treatments will be administered on an outpatient basis.

Pembrolizumab Dose Modification and Treatment Delay Guidelines

Adverse events (both non-serious and serious) associated with pembrolizumab exposure may represent an immunologic etiology. These adverse events may occur shortly after the first dose or several months after the last dose of treatment. Pembrolizumab must be withheld for drug-related toxicities and severe or life-threatening AEs as per **Table 1**. See **Section 6.3** and Events of Clinical Interest Guidance Document for supportive care guidelines, including use of corticosteroids

The following dose modification rules will be used with respect to potential toxicity. Toxicity will be assessed according to the NCI Common Terminology Criteria for Adverse Events Version 4.0 (CTCAE v4.0).

Table 1 Dose Modification Guidelines for Drug-Related Adverse Events: Pembrolizumab

Toxicity	Hold Treatment For Grade	Timing for Restarting Treatment	Discontinue Subject
Diarrhea/Colitis	2 ¹	Toxicity resolves to Grade \leq 1 ¹	Resume once improved to Grade \leq 1
	3	Toxicity resolves to Grade \leq 1	Toxicity does not resolve within 12 weeks of last dose or inability to reduce corticosteroid to 10 mg or less of prednisone or equivalent per day within 12 weeks
	4	Permanently discontinue	Permanently discontinue

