The End of Treatment and Follow-up visit procedures are listed in **Section 8**. After the end of treatment, each participant will be followed for 30 days for adverse event monitoring (serious adverse events will be collected for 90 days after the end of treatment as described in **Section 10.2**). Participants who discontinue for reasons other than progressive disease will have post-treatment follow-up for disease status until disease progression, initiating a non-study cancer treatment, withdrawing consent or becoming lost to follow-up. After documented disease progression each participant will be followed by telephone for overall survival until death, withdrawal of consent, or the end of the study, whichever occurs first.

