8.9 Long Term Follow-Up Evaluations (\pm 2weeks)

Participants will be monitored every 3 months for up to 4 years (telephone contact is acceptable). Monitoring will be performed to assess further therapies administered and survival.

Participants who are unavailable for follow-up evaluations should be classified as lost to follow-up for 1 of the following reasons:

- Lost to follow-up: For a participant to be considered lost to follow-up, the investigator must make two separate attempts to re-establish contact with the participant. The attempts to re-establish participant contact must be documented (e.g., certified letter).
- Death: Date and cause of death will be recorded for those participants who die within 30 days after last dose of study drug (telephone verification is acceptable).

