10.2.2 Reporting Serious Adverse Events

For the time period beginning when the consent form is signed until treatment allocation/randomization, any serious adverse event, or follow up to a serious adverse event, including death due to any cause that occurs to any participant must be reported within 24 hours to the Sponsor and within 2 working days to Merck Global Safety if it causes the participant to be excluded from the trial, or is the result of a protocol-specified intervention, including but not limited to washout or discontinuation of usual therapy, diet, placebo treatment or a procedure.

For the time period beginning at treatment allocation/randomization through 90 days following cessation of treatment, or 30 days following cessation of treatment if the participant initiates new anticancer therapy, whichever is earlier, any serious adverse event, or follow up to a serious adverse event, including death due to any cause whether or not related to the Merck product, must be reported within 24 hours to the Sponsor and within 2 working days to Merck Global Safety.

SAEs identified as an Unanticipated Problem by the Investigator must be reported. Please refer to **Section 10.7.2** for details on reporting Unanticipated Problems.

Additionally, any serious adverse event, considered by an investigator who is a qualified physician to be related to the investigational drug, that is brought to the attention of the

investigator at any time outside of the time period specified in the previous paragraph, also must be reported immediately to the Sponsor and to Merck.

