10.4.1 Reporting Events of Clinical Interest (ECIs)

ECIs (both non-serious and serious adverse events) identified in the Event of Clinical Interest Guidance Document from the date of first dose of pembrolizumab through 90 days following cessation of treatment, or 30 days following cessation of treatment if the participant initiates new anticancer therapy, whichever is earlier, need to be reported within 24 hours to the Sponsor and within 2 working days to Merck Global Safety, regardless of attribution to study treatment, consistent with standard SAE reporting guidelines.

Attn: Worldwide Product Safety

[contact]

Reporting of Overdose

All reports of overdose with and without an adverse event must be reported within 24 hours to the Sponsor and within 2 working days hours to Merck Global Safety. (Attn: Worldwide Product Safety; [contact]).

Reporting of Pregnancy and Lactation

Although pregnancy and lactation are not considered adverse events, it is the responsibility of investigators or their designees to report any pregnancy or lactation in a participant (spontaneously reported to them), including the pregnancy of a male participant's female partner

that occurs during the trial or within 120 days of completing the trial, or 30 days following cessation of treatment if the participant initiates new anticancer therapy, whichever is earlier. All participants and female partners of male participants who become pregnant must be followed to the completion/termination of the pregnancy. Pregnancy outcomes of spontaneous abortion, missed abortion, benign hydatidiform mole, blighted ovum, fetal death, intrauterine death, miscarriage and stillbirth must be reported as serious events (Important Medical Events). If the pregnancy continues to term, the outcome (health of infant) must also be reported.

Such events must be reported within 24 hours to the Sponsor and within 2 working days to Merck Global Safety. (Attn: Worldwide Product Safety; [contact]).

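### SAEs and ECIs are reportable to 90 days after treatment, but no scheduled contact asks about them after day 30 (±7), so new late events in patients not on new anticancer therapy are liable to be missed

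*Combined protocol and SAP*

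**What the plan says.** **Reporting windows.** Section 6.6 separates routine events, for which "each participant will be followed for 30 days for adverse event monitoring", from SAEs: "serious adverse events will be collected for 90 days after the end of treatment". Section 10.2.2 sets the SAE window "through 90 days following cessation of treatment, or 30 days following cessation of treatment if the participant initiates new anticancer therapy, whichever is earlier". Section 10.4.1 sets the ECI window, for serious and non-serious ECIs regardless of attribution, "from the date of first dose of pembrolizumab through 90 days following cessation of treatment", with the same cut to 30 days on new anticancer therapy. Footnote 2 of Tables 4 and 5 repeats the 90-day SAE window.

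**Scheduled enquiries.** The synopsis and the Adverse Events rows of Tables 4 and 5 end at Safety Follow-Up, 30 days (±7) after the last dose. Safety Follow-Up #2, at day 60 (±7), is a complete metabolic panel (CMP) with magnesium, "with blood work only being required (to follow-up on electrolytes"; neither table marks adverse events there. Of the three-monthly long-term contacts, 8.9 says: "Monitoring will be performed to assess further therapies administered and survival". Section 10.3 ties assessment for possible ECIs to each dose, so that prompt ends when dosing ends.

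**Expected timing.** Section 6.1.1 says of pembrolizumab-associated events that may be immunologic: "These adverse events may occur shortly after the first dose or several months after the last dose of treatment".

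**The concern.** A duty to report an event works only if the site learns of it. Up to day 30 the schedule supplies a question. After that, the longer windows for SAEs and ECIs have no scheduled question behind them.

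The adverse event profile of the combination is a primary objective (3.1), and 1.5 states that no data had been published on EGFR antibodies with anti-PD-1 therapy in metastatic colorectal cancer. Many ECIs in Table 10 are reportable from grade 2 without being serious. Such an event, treated away from the study site, could go unreported without anyone breaching the protocol. Any loss of this kind would push late-event frequencies down, in the class of event that the protocol itself expects to appear late.

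**Working it through.** The plan gives no figure for this point, so there is none to reproduce. The check compares windows with visits. I take the day of last dose (8.7, 8.8) and cessation of treatment (10.2.2, 10.4.1) as the same day 0.

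**1. Windows against visits, patient on no new anticancer therapy**

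| Days after last dose | Reportable | Scheduled contact | Event question? |
|---|---|---|---|
| 0 to 30 | routine AEs, SAEs, ECIs | Safety Follow-Up, day 30 (23 to 37) | yes |
| 31 to 90 | SAEs, ECIs | CMP with magnesium, day 60 (53 to 67) | no |
| about 90 | SAEs, ECIs to day 90 | first three-monthly contact (±2 weeks) | no: therapies and survival |

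Section 8.9 does not say when the three-month interval starts. If it runs from the last dose and three months is taken as 90 days, the first contact falls between day 76 and day 104, so it can come before the window closes.

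**2. Length of the gap.** Gap = 90 − day of the last event enquiry.
- Visit on day 30: 90 − 30 = 60 days; 60/90 = 67%.
- Visit on day 37: 90 − 37 = 53 days; 53/90 = 59%.
- Visit on day 23: 90 − 23 = 67 days; 67/90 = 74%.

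Once new anticancer therapy starts, the window is 30 days and the gap largely disappears: it is at most 30 − 23 = 7 days.

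**3. What the day-60 draw can show.** The panel in 8.8 includes AST, ALT, bilirubin, alkaline phosphatase, creatinine and glucose. It could reveal hepatic, renal or glucose abnormalities present at the draw. It has no symptom question and no thyroid tests, so it would not be expected to reveal colitis, pneumonitis, skin, neurologic or thyroid events.

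**4. Exposure during the gap (context only).** Section 1.4.1.2 gives a mean half-life of 26 days. With simple exponential decay, fraction remaining = 2^(−t/26): 0.45 at day 30, 0.20 at day 60 and 0.09 at day 90. This shows that exposure continues. It does not measure missed events.

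**5. Illustration of size.** The documents give neither a late-event rate nor the share that would surface without being asked for. Assume that all 42 patients keep the full window, that a fraction q of 2% to 10% have a late SAE or ECI, and that a fraction s of 50% to 80% of these are notified spontaneously.
- Expected missed = 42 × q × (1 − s): from 42 × 0.02 × 0.2 = 0.17 to 42 × 0.10 × 0.5 = 2.1.
- Chance of missing at least one = 1 − [1 − q(1 − s)]^42: from 16% to 88%.
- If s = 100%, none is missed.

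Patients who start new therapy leave the full window, so 42 is an upper limit on the number at risk. One missed patient lowers an event rate by 1/42 = 2.4 percentage points.

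Sample size, type I error and power rest on response and 6-month PFS and are unaffected.

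**The case against.** **Reporting is mandatory.** SAEs and ECIs must reach the sponsor within 24 hours throughout the window, and a reporting window longer than the visit schedule is not a contradiction. That is right. But the duty covers events the site knows of, and follow-up to resolution (8.7, 10.5, 10.6) concerns events already identified, not new onsets.

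**Other contacts exist.** Patients who stop for reasons other than progression are followed for disease status (6.6), and survival contacts would bring a death to light. This lowers the risk. Neither provision includes an event question, and 8.9 asks for cause of death only within 30 days of the last dose. The separate ECI guidance document may say more about finding events; it is not part of these documents.

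**The heading of 8.8 begins with adverse events.** Its body requires blood work only, and neither table marks adverse events at that visit. The list in 8.7 lacks the adverse-event line that Table 4 places there, so the words look like a displaced bullet.

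**Stronger readings that a reader might infer, and that the documents do not support:**
- *Late events are under-counted.* Without a late-event rate or a spontaneous-capture rate, only a liability is shown. Section 12.4.1 tabulates across all cycles and does not say whether post-treatment events enter.
- *Two thirds of the window is uncovered for the whole trial.* The figure applies only to patients who start no new anticancer therapy, and the documents do not say how many that is.
- *Late hepatitis would go unseen.* The day-60 panel could show it, and 10.3 accepts protocol-specified laboratory testing as a route to the liver-injury ECI.
- *Concomitant medication after day 30 needs its own visit.* Under 6.2.1 and 10.6 that record follows from the event once it is known.
- *A visit on day 23 cuts the routine period short.* Routine events stay reportable to day 30 whatever the visit date (10.1.3).

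**Conclusion.** The concern holds as a mismatch between the reporting window and the schedule. For a patient not on new anticancer therapy, more than half of the 90-day SAE/ECI window passes without a scheduled event question, whichever day the Safety Follow-Up visit falls. What is exposed is the ascertainment of new, symptom-based events after that visit. The comparison of text and tables is firm. The effect on the reported adverse event profile is a plausible downward bias of unknown size; the range in the illustration depends entirely on its assumptions. The point merits a schedule correction and gives no ground to question the efficacy design.

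**What to change.** - **8.8 and Tables 4 and 5:** add an SAE/ECI enquiry to Safety Follow-Up #2, at the blood draw or by telephone.
- **8.9 and the long-term column of both tables:** time the first long-term contact at or shortly after day 90 from the last dose. Add an SAE/ECI question covering the period since the previous enquiry for patients not on new anticancer therapy. Record the start date of any new therapy, since it decides which window applied.
- **12.4.1:** state that events in the post-treatment reporting window enter the tabulation.

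With both questions in place, the span without an enquiry falls to about zero. The cost is a few questions at contacts that already exist, plus wording in two tables and three sections. Reported late-event rates may rise. Sample size, type I error and power do not change.
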